5.5.4.1 Colony Stimulating Factors

All patients should receive G-CSF 5 mcg/kg SC daily from day 12 until achievement of an ANC of $> 1.5 \times 10^9/\text{lt}$.

5.5.4.2 Antimicrobial Supportive Care

Antibacterial, antifungal and antiviral prophylaxis and treatment should follow conventional guidelines or institutional protocols. Patients should receive an oral Quinolone, Fluconazole, and Acyclovir to prevent infection once the ANC drops below 1000 mm^3 .

Management of immunosuppression and donor lymphocyte infusions: Therapy will be directed to promote engraftment, and minimize GVHD without undue immunosuppression.

5.5.4.3 Treatment of Acute GVHD

Patients who develop Grade 2 or greater acute GVHD will receive methylprednisolone or prednisone at least 2 mg/kg daily and subsequently tapered according to institutional standard. Other immunosuppression may be administered as needed.

5.5.4.4 Immunosuppression

Patients with < 5% engraftment by day 35 may have immunosuppression tapered early in accordance with institutional standards.

5.5.4.5 Treatment of Residual Disease

Patients with evidence of residual disease as defined by clinical, radiological, cytogenetic or molecular techniques may have immunosuppression tapered rapidly and may subsequently receive treatment with 10^6 to 10^8 CD3+ donor lymphocyte cells/kg ("donor lymphocyte infusion") as often as every 6-12 weeks for up to 3 courses at the discretion of the treating physician and in accordance with institutional standards.

If a patient experiences a creatinine > 3, Tacrolimus will be decreased whenever possible. If in the judgment of the primary investigator Tacrolimus cannot be maintained at an adequate level then other immunosuppression should be added.

5.5.4.5.1 GVHD Prophylaxis

Standardizing GVHD prophylaxis regimen will be utilized comprising ATG, Tacrolimus, and methotrexate. See Section [5.5](#).

5.5.4.5.2 Tacrolimus Administration

Tacrolimus will be started 2 days before the marrow infusion at a dose of 0.03 mg/kg/day intravenously infused continuously over a period of 24 hours (Institutional standard allowed if equivalent). IV tacrolimus can be discontinued when patient starts to eat and PO tacrolimus substituted at a dose four times the IV dose (0.12 mg/kg) in two divided doses. Monitor blood concentrations to keep in therapeutic range per institutional guidelines. Unless toxicity is encountered, tacrolimus can be

Rev. 2/13

Rev. 2/12

continued at the same dose until day 100, after which the drug can be tapered and discontinued on day 180 after grafting.

5.5.4.5.3

Methotrexate Administration

Methotrexate is to be administered at doses of 5 mg/m² I.V. on days 1, 3, 6 and 11.

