CR1 (personal communication, Drs. [name] & [name]), we plan to employ an identical busulfan-fludarabine conditioning regimen with similar GVHD prophylaxis. This will allow comparability of our AlloSCT results with those of the BMT CTN 0502 study, but in a more uniformly-treated population. However, the systematic early consideration of AlloSCT from the time of diagnosis in E2906, and inclusion of HLA-typing at presentation, has an important advantage over previous pilot RIC studies, and will allow a more definitive evaluation of the role of AlloSCT in this population.

The non-ablative Flu-Cy conditioning regimen has limited anti-leukemic activity, and although the same may be said for other regimens the proposed reduced-intensity busulfan-fludarabine regimen has the advantage of having been used successfully in a recent multi-center study. Both regimens share low morbidity and non-relapse-related mortality (NRM), and both share the intent of inducing early engraftment and a GVL effect.

As applied to better matched, less heavily-treated AML patients in CR after only 1 regimen as proposed in E2906, we may expect superior results. In contrast more intensive preparative regimens have often been substantially more toxic^{58,67}.

1.2.1 In Summary, these observations strongly suggest that allogeneic hematopoietic transplantation may yield durable remissions in older AML patients who would without transplant have died of their leukemia. Thus the formal testing of this therapy in a large series of patients 'biologically' randomized to receive or not to receive transplantation based on donor availability is logical and timely. Disease free and overall survival will be examined in these treatment groups in comparison with patients who are treated with chemotherapy in a 'donor vs. no donor' analysis.

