5.1.7.4.2 Stem Cells

Cryopreserved stem cells are rapidly thawed at 37°C and immediately infused 36-48 hours after the last dose of Cyclophosphamide.

5.1.7.4.3

PBSC Infusion: The cells are not washed before reinfusion, and the osmolality of the cell suspension requires the use of a flowing central venous catheter. Before reinfusion of PBSC, hydration must be maintained to have an output of at least 3 cc/kg/hour. Emergency drugs (Benadryl, epinephrine, Solu-Medrol) in appropriate doses must be at the bedside. Baseline vital signs, forced vital capacity and EKG are recorded.

Rev. 2/12

Fifteen minutes prior to administration of the thawed PBSC, the patient is to receive:

- 50 mL of 25% mannitol solution IV
- 50 mg of diphenhydramine IV
- 250 mg of hydrocortisone IV
- An antiemetic drug of choice (optional)

NOTE: Institutional standard allowed for PBSC pre-meds.

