Rev. 2/12		
Patients should receive an oral Quinolone, Fluconazole or equivalent based on institutional standard, and Acyclovir to prevent infection once the ANC drops below 1000 mm³.
 
GM-CSF 250 mcg/m²/day by intravenous or subcutaneous injection starting one day after the last dose of clofarabine through recovery of absolute neutrophil count (ANC) \geq 500 cells/mcL is sustained for 3 consecutive days. The dose may be rounded to the nearest vial size.

Rev. 2/12

OR
G-CSF 5 mcg/kg/day by either intravenous or subcutaneous injection starting one day after the last dose of clofarabine, through recovery of absolute neutrophil count (ANC) \geq 500 cells/mcL is sustained for 3 consecutive days. The dose may be rounded to the nearest vial size.

OR
Pegfilgrastim 6 mg SC on day 6 (1 day after completing the last dose of clofarabine).

5.5.4 **Arm G** Supportive Care for Allogeneic Transplant

Rev. 2/13

NOTE: Patients must be premedicated with acetaminophen 650 mg P0, diphenhydramine 25-50 mg P0/IV prior to thymoglobulin, and methylprednisolone 1 mg/kg at initiation and midway through thymoglobulin administration each day.

Patients will be evaluated on an outpatient basis for evidence of toxicity, in particular graft vs. host disease (GVHD) and cytopenias.

GVHD Prophylaxis

Tacrolimus dosing is to be based on target serum levels of 5-10 ng/mL. **Serum levels are not to exceed 15 ng/mL.** Tacrolimus is to be initiated on Day -2 with a suggested starting dose of 0.03 mg/kg P0 BID (Institutional standard allowed if equivalent). Begin tapering between Day +90 to +120 in the absence of GVHD as tolerated with a goal of stopping by Day +150 to +180. The rate of taper will be adjusted for the presence of signs and symptoms of GVHD. In patients who are unable to take oral tacrolimus, the intravenous dose is generally 1/4 to 1/3 of the oral dose.

Please note that concurrent use of agents such as itraconazole, voriconazole or fluconazole (at doses $>$ 200 mg) may inhibit the metabolism of tacrolimus, and thus increase tacrolimus levels. Hence, it is recommended to check tacrolimus levels twice weekly when these agents are initiated concurrently. In addition, the initial dose of tacrolimus may be decreased according to institutional policies.

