8.6.3 Administration

Tacrolimus is to be initiated on Day -2. Begin tapering between Day +90 to +120 in the absence of GVHD as tolerated with a goal of stopping by Day +150 to +180. See protocol text for tapering instructions, and for instructions for patients who are unable to take oral tracolimus.

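### Arm G tacrolimus has two conflicting starting instructions: by the protocol's own oral-to-IV conversion the starting doses differ 1.5- to 2.0-fold, and nothing says which governs

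*Combined protocol and SAP*

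**What the plan says.** **Oral start.** The transplant schema and Section 5.5.4 agree with each other. In Section 5.5.4: "Tacrolimus is to be initiated on Day -2 with a suggested starting dose of 0.03 mg/kg P0 BID". For patients who cannot take the drug by mouth, the same section adds that "the intravenous dose is generally 1/4 to 1/3 of the oral dose". The level target is 5-10 ng/mL with a ceiling of 15 ng/mL, given in the schema, in the GVHD prophylaxis text of Section 5.5.4 and again in its toxicity-management text.

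**Intravenous start.** Section 5.5.4.5.2 begins two days before infusion, "at a dose of 0.03 mg/kg/day intravenously infused continuously over a period of 24 hours". Once the patient is eating, it has "PO tacrolimus substituted at a dose four times the IV dose (0.12 mg/kg) in two divided doses". Levels are to be kept in a range set by institutional guidelines, with no number given.

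**Shared flexibility.** Sections 5.5.4 and 5.5.4.5.2 both let a site use its institutional standard if that is equivalent.

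**Intent.** Section 5.5.4.5.1 says: "Standardizing GVHD prophylaxis regimen will be utilized comprising ATG, Tacrolimus, and methotrexate". It then refers back to Section 5.5, which contains both instructions. Section 8.6.3 sends the reader to the protocol text for the details of tapering and of non-oral dosing.

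**The concern.** Both instructions start on the same day for the same patients, but they differ in default route and in dose. A site that follows Section 5.5.4 and a site that follows Section 5.5.4.5.2 are each compliant, yet they begin at different exposures. The equivalence allowance does not help, because it needs one reference dose and there are two.

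Two things are at stake.

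- **Patient safety.** The opening days are when the written doses matter most. Azole prophylaxis also starts on Day -2. Section 5.5.4 warns that azoles can raise tacrolimus levels and permits a lower initial dose, whereas Section 5.5.4.5.2 says nothing on this.
- **Interpretation.** Objective 2.2.2 covers engraftment, acute and chronic GVHD, transplant-related mortality and the effect on survival. Section 1.2 says of its choice of conditioning and similar GVHD prophylaxis: "This will allow comparability of our AlloSCT results" with an earlier multicentre study. A reader of those results should be able to tell how tacrolimus was started.

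**Working it through.** No sample-size or power formula applies. The check puts both instructions on one daily scale.

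**Inputs**
- Oral start: 0.03 mg/kg twice daily (schema; Section 5.5.4).
- IV dose as a share of the oral dose: 1/4 to 1/3 (Section 5.5.4).
- IV start: 0.03 mg/kg/day (Section 5.5.4.5.2).
- Oral switch dose: four times the IV dose, stated as 0.12 mg/kg (Section 5.5.4.5.2).
- Oral bioavailability: about 25% (Section 8.6.1), as a cross-check.

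**Step 1. Reproduce the stated figure.** 4 × 0.03 = 0.12 mg/kg/day. This matches Section 5.5.4.5.2, reading its oral figure as a daily total because it is a multiple of a daily dose.

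**Step 2. Oral start as a daily dose.** 2 × 0.03 = 0.06 mg/kg/day.

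**Step 3. Convert to an IV equivalent by the rule in Section 5.5.4.**
- 0.06 × 1/4 = 0.015 mg/kg/day
- 0.06 × 1/3 = 0.020 mg/kg/day

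**Step 4. Compare the starting doses.**

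| Conversion | Section 5.5.4 as IV (mg/kg/day) | Section 5.5.4.5.2 IV (mg/kg/day) | Ratio |
|---|---|---|---|
| 1/4 | 0.015 | 0.030 | 2.0 |
| 1/3 | 0.020 | 0.030 | 1.5 |

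The 25% bioavailability gives 0.06 × 0.25 = 0.015, again a ratio of 2.0. Without any route conversion the order reverses: 0.06 is twice 0.03.

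**Step 5. Other elements, side by side.**
- *Start day:* Day -2 in both.
- *Level target:* 5-10 ng/mL, ceiling 15, in the schema and twice in Section 5.5.4; an unnumbered institutional range in Section 5.5.4.5.2.
- *Taper start:* Section 8.6.3 has "Begin tapering between Day +90 to +120 in the absence of GVHD as tolerated", and Section 5.5.4 agrees. Section 5.5.4.5.2 allows the same dose to day 100 and a taper after that. The windows overlap from about Day +100 to Day +120.
- *Taper end:* Day +150 to +180 against day 180. These meet at Day +180.
- *ATG and methotrexate:* the same dose and days wherever they are stated.
- *Monitoring:* Section 7.2, note D, requires levels twice weekly from Day -2 to Day +28, then weekly to Day +150 or until the drug is stopped.

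**The case against.** The strongest reply is that the protocol never meant to fix the dose rigidly. The oral dose is only suggested, an equivalent institutional standard is allowed, and dosing follows measured levels from Day -2 onwards, so a difference at the start should be short-lived. This stands as a limit on size and duration. It does not remove the contradiction: by the protocol's own conversion the two written doses are not equivalent to each other, and Section 5.5.4.5.2 gives its dose as an instruction, not a suggestion.

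A reader might also infer more than the text supports:

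- *That the whole prophylaxis regimen is undefined.* It is not. ATG, methotrexate and the Day -2 start agree; only tacrolimus is affected.
- *That the taper schedules conflict.* One schedule can satisfy every section, and the wording in Section 5.5.4.5.2 is permissive.
- *That there are two competing level targets.* Section 5.5.4.5.2 gives no rival number, and Section 5.5.4 states its ceiling without exception. The gap is an omission that invites misreading.
- *That starting doses differ exactly two-fold on the oral scale.* 0.12 against 0.06 does give 2.0, but 0.12 mg/kg/day is a later switch dose, so this does not compare two starting doses.
- *That the comparison with the earlier study fails.* Section 1.2 claims identical conditioning but only similar GVHD prophylaxis.
- *That the primary result is affected.* Section 9.2 censors patients at transplant in the primary survival analysis.

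**Conclusion.** The concern holds for the starting route and dose of tacrolimus in Arm G. The two starting doses differ 1.5- to 2.0-fold, on the assumption that the general conversion in Section 5.5.4 applies. No cross-reference says which instruction governs. The missing level target in Section 5.5.4.5.2 is a secondary gap of wording.

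The planned number of patients concerned is 8% of 747, or 0.08 × 747 ≈ 60. The documents do not give the actual number transplanted. Section 9.5 records that Step 1 accrual was suspended at 727 patients, and the conditional reopening it describes is for consolidation and the maintenance randomization. Much of the remaining value of a correction may therefore lie in clear reporting. No power, error-rate or sample-size figure depends on this point.

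A separate and smaller inconsistency sits nearby. Section 5.1.7.4.2 has stem cells "immediately infused 36-48 hours after the last dose of Cyclophosphamide", a drug absent from the preferred fludarabine-busulfan-ATG regimen in Section 5.1.7.3. Because Section 5.1.7.3 permits alternative conditioning after discussion and Section 5.1.7.4 permits institutional infusion practice, this is a matter of wording to reconcile. It adds nothing to the tacrolimus point.

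**What to change.** - **One instruction.** The sponsor and the transplant chairs should reconcile the schema, Section 5.5.4 (both its prophylaxis and its toxicity-management text), Section 5.5.4.5.2 and Section 8.6.3. The result should be a single tacrolimus instruction covering route, starting dose, IV/oral conversion and level target, stated once and cross-referenced elsewhere. It should name the reference against which an institutional standard counts as equivalent. This review takes no view on which dose, route or target is right.
- **Infusion timing.** Separately, reconcile Section 5.1.7.4.2 with Section 5.1.7.3.
- **Patients already transplanted.** When GVHD and transplant-related mortality are reported, state descriptively which starting instruction was used. A formal comparison by instruction is not advised: it would split roughly 60 planned patients into small groups chosen by site and blurred by level adjustment.

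The cost is a short amendment and one descriptive data item for transplanted patients, with no new procedures and no additional patients.

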5.6 Duration of Therapy

Patients will receive protocol therapy unless:

- Extraordinary Medical Circumstances: If at any time the constraints of this protocol are detrimental to the patient's health, protocol treatment should be discontinued. In this event submit forms according to the instructions in the E2906 Forms Packet.
- Patient withdraws consent.

5.6.1 Induction

The induction phase is considered to include the period of time from when a patient is enrolled on trial until one of the following endpoints:

- Death.
- Failure to achieve marrow aplasia after two courses of induction therapy or after one course of induction and judged to be unable to receive any further therapy.
- Achievement of CR and discharge from the hospital. Any repeat hospitalization within two weeks of induction needs to be reported.
- Patients who fail to experience recovery of peripheral blood counts to remission status by day 56 will undergo a repeat marrow aspirate and biopsy. Patients should be followed, at a minimum, with weekly CBCs until it is determined that there is recovery of peripheral blood counts, refractory AML, or death.
- Patient withdraws consent.
- A toxicity which in the opinion of the investigator precludes further protocol therapy. The patient should be followed until resolution of the toxicity.

5.6.2 Consolidation Cycle 1

Consolidation I is considered to include the period of time from when a patient receives therapy until one of the following endpoints:

- Death
- Recovery of peripheral blood counts and discharge from the hospital. Any repeat hospitalization within two weeks of discharge after Consolidation I needs to be reported

Patients who do not begin Consolidation II within 60 days of recovery are ineligible for further protocol therapy.

5.6.3 **Consolidation Cycle 2**

The Second Consolidation Cycle is considered to include the period of time from when a patient receives therapy until one of the following endpoints:

- Death.
- Recovery of peripheral blood counts and discharge from the hospital. Any repeat hospitalization within two weeks of discharge after Consolidation II needs to be reported.

Rev. 2/13

5.7 **Duration of Follow-up**

Surviving patients will be followed for at least 5 years. Following completion of consolidation, all patients will have a CBC performed monthly ***as well as a BM biopsy/aspirate performed every 3 months, for the first 24 months*** (including 12 months of observation or maintenance decitabine in 2nd randomization), then q3 months for ***the next*** 2 years, then q6 months. Following 5 years, patients will have a CBC performed annually and followed for survival.

For this protocol, all patients, including those who discontinue protocol therapy early, will be followed for response until progression, even if non-protocol therapy is initiated, and for survival for 5 years from the date of registration. All patients must also be followed through completion of all protocol therapy.

6. Measurement of Effect

6.1 Complete Remission (CR)

Requires that all of the following be present:

6.1.1 Peripheral Blood Counts

6.1.1.1 Neutrophil count $\geq 1.0 \times 10^9 / L$.

6.1.1.2 Platelet count $\geq 100 \times 10^9 / L$.

6.1.1.3 Reduced hemoglobin concentration or hematocrit has no bearing on remission status.

6.1.1.4 Leukemic blasts must not be present in the peripheral blood.

6.1.2 Bone Marrow Aspirate and Biopsy

6.1.2.1 Cellularity of bone marrow biopsy must be $> 20\%$ with maturation of all cell lines.

6.1.2.2 $< 5\%$ blasts by morphologic review.

6.1.2.3 Auer rods must not be detectable.

6.1.3 Extramedullary leukemia, such as CNS or soft tissue involvement, must not be present.

6.2 Complete Remission incomplete (CRI)

All the same response criteria in peripheral blood and bone marrow as CR with the exception that there is incomplete platelet recovery (platelets $> 50 \times 10^9 / L$ independent of platelet transfusions) over a period of observation without evidence of ongoing platelet recovery and no sooner than day 35 after the preceding cycle of treatment.

Rev. 8/13

6.2.1 Patients who achieve criteria for CR or CRI and who have recovered from the effects of therapy but who have **< 20% cellularity in BM** will be deemed a "Hypocellular CR/CRI" and will be allowed to continue protocol therapy at the discretion of the Investigator and after discussion with the Study Chair as long as they meet other eligibility criteria for Step 2

6.3 Partial Remission (PR)

6.3.1 Requires that all of the criteria for complete remission be satisfied except that the bone marrow may contain $> 5\%$ blasts but $< 25\%$ blasts.

6.3.2 If all other criteria for CR are met, then a value of $\leq 5\%$ blasts with Auer rods or abnormal morphology is considered a partial remission.

6.4 Relapse

Relapse following complete remission is defined as:

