2.2 Secondary Objectives

2.2.1 To evaluate complete remission (CR) rates, duration of remission, and toxicity/treatment-related mortality of clofarabine in comparison with standard therapy (daunorubicin & cytarabine) in newly-diagnosed AML patients age \geq 60 years.

2.2.2 To evaluate the feasibility of consolidation with reduced-intensity conditioning and allogeneic hematopoietic stem cell transplantation from HLA-identical donors in patients who achieve a response to induction therapy, including the incidence of successful engraftment, acute and chronic graft-versus-host disease, transplant-related mortality, and its impact on overall survival in comparison to patients receiving chemotherapy.

2.2.3 To evaluate the duration of remission and disease-free survival of patients in complete remission following completion of consolidation therapy who are subsequently randomized to receive scheduled low-dose decitabine maintenance in comparison with observation.

2.2.4 To perform expression and methylation profiling on all patients receiving decitabine and to correlate their integrated epigenetic signatures with response to decitabine.

2.2.5 To examine the epigenetic profiles of remission marrow in patients randomized to observation vs. decitabine to determine whether epigenetic signature of apparently morphologically normal bone marrow is predictive of relapse or response to decitabine maintenance.

2.2.6 To explore the possible association of response to clofarabine with ABC-transporter P-glycoprotein (Pgp).

2.2.7 To assess the intensity of expression of CXCR4 on diagnostic leukemia cells and to correlate this parameter with other established prognostic factors

2.2.8 To assess the entire spectrum of somatic mutations and affected pathways at diagnosis of AML and elucidate the association between gene mutation and outcome.

2.2.9 To examine the impact of smoking, obesity, regular acetaminophen use, regular aspirin use, benzene exposure, living in a rural/farm environment and some other underlying exposures and lifestyle factors associated with AML development on OS.

Rev. 2/13

Rev. 2/12

Rev. 2/12

Rev. 2/13

Rev. 2/13

2.2.10 To investigate potential correlative results between array CGH findings and acute myeloid leukemia patient characteristics.

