6.4.1 Peripheral Blood Counts

6.4.1.1 Reappearance of blasts in the blood.

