6.4.2 Bone Marrow Aspirate and Biopsy

6.4.2.1 Presence of > 5% blasts, not attributable to another cause (e.g., bone marrow regeneration).

6.4.2.2 If there are no circulating blasts and the bone marrow contains 5% to 20% blasts, then a repeat bone marrow performed \geq 1 week later documenting more than 5% blasts is necessary to meet the criteria for relapse.

Rev. 2/12 6.5 Leukemia Free State

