6.5.3 Flow Cytometry of BM Aspirate

Rev. 2/12 6.5.3.1 If one or more unique leukemia-associated immunophenotypes (LAIP) were identified at diagnosis, minimal residual disease (MRD) levels will be analyzed by multiparameter flow cytometry.

Rev. 2/12 6.5.3.2 Immunologic MRD must be below the level of detection (< 0.001) to qualify for "Leukemia-Free State".

Rev. 2/12 6.5.3.3 Any detectable immunologic MRD levels will be quantified and retrospectively correlated with relapse-free and overall survival.

6.5.4 Extramedullary leukemia must not be present.

6.5.5 If indeterminant, the BM Aspirate & biopsy should be repeated 1 week later.

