The induction CR rates will be monitored to allow for early stopping in favor of inferiority using the repeated confidence interval methodology described by Jennison and Turnbull (123). Interim analyses will be conducted for induction CR rates when induction response data is available on 25%, 45%, 65%, 85% and 100% of patients. At each interim analysis, the two-sided 95% repeated confidence interval on the difference of CR rate (CR rate of standard treatment – CR rate of clofarabine) will be computed. This repeated confidence interval uses the critical value from a truncated O'Brien-Fleming error spending rate function with an overall one-sided 2.5% error rate. If the confidence interval lies entirely above 0, the induction randomization may need to be stopped due to the inferiority of clofarabine and subsequent patients will directly be assigned to standard treatment arm.

Another objective of this trial is to determine the effect of decitabine on disease free survival (DFS) as a maintenance therapy in comparison with observation. DFS is defined as the time from the second randomization to relapse or death without relapse. If 25% of patients who do not receive allogeneic transplant go through the second randomization, there will be 172 patients = randomized to either the decitabine arm or the observation arm.

We assume that the long-term cure rate for the observation arm is 10% and the median DFS in the non-cured group is 7 months. The study will have 90% power to detect approximately a 36% reduction in the DFS hazard rate in the decitabine maintenance therapy arm. This power calculation is based on a one-sided log-rank test at the significance level of 0.1 and assumes 5 years of accrual and 2 years of follow-up after the completion of the accrual. The number of DFS events needed is 140. The primary analysis of DFS will be an intention-to-treat analysis and will use a one-sided log rank test stratified on the induction and consolidation therapy and on patient age and cytogenetics.

Another secondary objective of this study is to evaluate the impact of consolidation with non-ablative conditioning and allogeneic hematopoietic stem cell transplantation with an HLA-identical sibling on overall survival in patients who achieve a 'morphologic leukemia-free state'.

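### Section 6.4 gives relapse no extramedullary criterion, so an isolated extramedullary recurrence is not itself a DFS event and the event is dated late

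*Combined protocol and SAP*

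**What the plan says.** **Relapse.** Section 6.4 begins "Relapse following complete remission is defined as" and gives two routes. The blood route (6.4.1) is "Reappearance of blasts in the blood". The marrow route (6.4.2) is "Presence of > 5% blasts, not attributable to another cause", with a repeat marrow at least one week later when the count is 5% to 20% and there are no circulating blasts. Section 6.5 follows directly.

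**Remission.** Section 6.1.3 sets a condition for CR: "Extramedullary leukemia, such as CNS or soft tissue involvement, must not be present". Section 6.5.4 sets the same condition for leukemia-free state: "Extramedullary leukemia must not be present".

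**Endpoints.** Section 9.4 states: "DFS is defined as the time from the second randomization to relapse or death without relapse". It adds no relapse definition of its own. Objective 2.2.3 reads in part "To evaluate the duration of remission and disease-free survival of patients in complete remission", and objective 2.2.1 also lists duration of remission. Neither says which event ends a remission.

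**Follow-up.** Maintenance patients have monthly blood counts and examinations for 24 months (5.1.8.1), and a marrow every 3 months over the same period (5.7; Section 7.1, notes 8 and 17). Clinical evidence or symptoms of relapse are a reason for a marrow (Section 7.1, notes 13 and 17).

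**The concern.** The condition that must hold to enter remission is wider than the condition that ends it. Extramedullary leukemia bars a patient from CR but does not count as loss of CR. Following the stated rule, a patient with proven CNS or soft-tissue recurrence, clear blood and a clear marrow is counted as disease-free.

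DFS from the second randomization is the endpoint of the decitabine-versus-observation question. Under Section 9.5 it also feeds the conditional-power decision on reopening and the final analysis, at about 125 events if the study reopens or about 90 if it closes. No blinding is described. One site may apply Section 6.4 literally and another may record relapse on clinical grounds, so the same clinical event could carry different dates.

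**Working it through.** **1. Classify one patient under each definition.** Take a patient randomized in CR who develops documented soft-tissue or CNS leukemia, with no blasts in the blood and fewer than 5% in the marrow.

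| Definition | Section | Met? |
|---|---|---|
| CR | 6.1.3 | No: extramedullary disease is present |
| PR | 6.3.1 | No: every CR criterion other than marrow blasts must hold |
| Leukemia-free state | 6.5.4 | No: extramedullary disease is present |
| Relapse, blood | 6.4.1 | No |
| Relapse, marrow | 6.4.2 | No |

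The patient fits no response category and has not relapsed. No other section counts extramedullary recurrence as relapse. The notes to Section 7.1 prompt a marrow, and a negative marrow leaves no event.

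**2. Effect on the event date.** Let E be the date of extramedullary recurrence, B the date of blood or marrow relapse, and D the date of death.

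- As written, the DFS event date is min(B, D).
- With an extramedullary criterion, it is min(E, B, D).
- When E comes first, the date is late by min(B, D) − E.
- The event is missed only if min(B, D) falls after the analysis cut-off.

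**3. The plan's own figures.** The inputs come from Sections 9.4 and 9.5. With d events, the approximate power of a one-sided log-rank test with equal allocation (Schoenfeld) is Φ(½√d·|ln HR| − z₁₋α).

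- Original design, d = 140, HR 0.64, α = 0.1: ½ × 11.832 × 0.4463 − 1.2816 = 1.359, power 91.3% (stated 90%).
- If reopened, d = 125, HR 0.63, α = 0.1: ½ × 11.180 × 0.4620 − 1.2816 = 1.301, power 90.3% (stated about 90%).
- If closed, d = 90, HR 0.64, α = 0.15: ½ × 9.487 × 0.4463 − 1.0364 = 1.080, power 86.0% (stated about 85%).

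For 90% power in the original design, Freedman's formula gives 137 events and Schoenfeld's gives 132, against 140 stated. The plan's figures hold and are not in dispute.

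**4. Illustration of missed events.** The documents give no rate of isolated extramedullary recurrence. The shares below are assumptions. They treat the events as wholly missed, equally in both arms, with the hazard ratio unchanged.

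| Share missed | Of 125: events left | Power | Of 90: events left | Power |
|---|---|---|---|---|
| 2% | 122.5 | 89.9% | 88.2 | 85.5% |
| 5% | 118.75 | 89.2% | 85.5 | 84.8% |
| 10% | 112.5 | 87.9% | 81 | 83.4% |

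In practice most such events would be late rather than missed, so this overstates the loss for a given share of affected patients.

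**The case against.** The best reply is that the gap rarely matters and partly closes itself. Monthly counts and 3-monthly marrows would pick up later blood or marrow involvement. Section 5.7 continues response follow-up even after non-protocol treatment starts, and death is always an event. Documented CNS disease is excluded at entry (3.2.6.9). DFS is secondary, and OS, CR rate and 30-day mortality are untouched. All of this stands, and it limits the size of the problem. It does not make extramedullary recurrence an event or give it a date.

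Some stronger readings are tempting but not supported:

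- **That these patients never have a DFS event.** Section 9.4 also counts death without relapse, and later blood or marrow relapse counts under 6.4. Only the extramedullary recurrence itself is left out.
- **That a number of affected events can be stated.** The documents give no rate. A proportion of relapses taken from outside also cannot be applied to all 90 or 125 DFS events, because those include deaths without relapse.
- **That the arms are affected differently.** Nothing in the documents suggests this.
- **That CRi patients have no relapse definition.** Section 6.4 speaks of complete remission, while Section 3.2.8.2 admits CR or CRi. But Section 6.2 names CRi as a form of complete remission, and objective 2.2.3 uses the term for the whole randomized group. This is an editorial point.

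**Conclusion.** The concern holds as a defect in the endpoint definition. For an isolated extramedullary recurrence after CR or CRi, Section 6.4 dates the DFS event late, and misses it only when neither blood or marrow relapse nor death occurs before the analysis. That duration of remission is affected in the same way is an inference, since that endpoint has no event definition and would presumably rest on Section 6.4.

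The effect on power is probably small: about 90% becomes 88% to 90% if an assumed 2% to 10% of 125 events were missed. The case for acting rests on validity and consistent dating, not on power. The primary OS comparison is unaffected.

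**What to change.** Add a Section 6.4.3 along these lines: *new or recurrent extramedullary leukemia, documented by cytology, histology or imaging when clinically investigated, counts as relapse; the date is that of first documentation.* State in 6.4 that the definition applies after CR or CRi, and that it governs both DFS and duration of remission in all arms. No scheduled procedure is added.

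Section 9.5 reports 120 patients already randomized to maintenance. Re-date these only where existing records allow. Do it blind to arm and before any further DFS analysis, including the conditional-power calculation if that is still pending. Report DFS under the current Section 6.4 definition as a sensitivity analysis.

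The cost is a short addition to Section 6.4 and a blinded check of relapse records. The Forms Packet is not part of these documents, so whether it records the site of relapse is unknown, and some patients may not be re-datable. The downside is that an endpoint is being clarified, in a small way, after some outcome data exist. The blinded review and the sensitivity analysis address that.
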